### **5.8 Duration of Therapy**

If at any time the constraints of this protocol are considered to be detrimental to the patient's health and/or the patient no longer wishes to continue protocol therapy, the protocol therapy should be discontinued and the reason(s) for discontinuation documented in the case report forms.

In the absence of treatment delays due to adverse events, treatment may continue for 2 months or until one of the following criteria applies:

- Documented and confirmed disease progression
- Death
- Adverse event(s) that, in the judgment of the investigator, may cause severe or permanent harm or which rule out continuation of study drug
- General or specific changes in the patient's condition render the patient unable to receive further treatment in the judgment of the investigator
- Suspected pregnancy
- Serious non-compliance with the study protocol
- Lost to follow-up
- Patient withdraws consent
- Investigator removes the patient from study
- The Siteman Cancer Center decides to close the study

Patients who prematurely discontinue treatment for any reason will still be followed as indicated in the study calendar.

### **5.9 Duration of Follow-up**

Patients will be followed at least every 6 months for 2 years or until death, whichever occurs first. Patients removed from study for unacceptable adverse events will be followed until resolution or stabilization of the adverse event. Patients will return to the clinic for routine post-transplant visits during the first 6 months of follow-up. After the first 6 months, patients can be followed either in person via clinic visit or through a phone call or medical records review.

### **5.10 Lost to Follow-Up**

A participant will be considered lost to follow-up if he or she fails to return for 6 weeks following a scheduled visit and is unable to be contacted by the study team.

The following actions must be taken if the participant fails to return to clinic for a required study visit:

- The study team will attempt to contact the participant and reschedule the missed visit within 6 weeks and counsel the participant on the importance of maintaining the assigned visit schedule and ascertain if the participant wishes to and/or should continue in the study.
- Before a participant is deemed lost to follow-up, the investigator or designee will make every effort to regain contact with the participant (where possible, 3 telephone calls and, if necessary, a certified letter to the participant's last known mailing address). These contact attempts should be documented in the participant's medical record or study file.
- Should the participant continue to be unreachable, he or she will be considered to have withdrawn from the study with a primary reason of lost to follow-up.

## 6.0 DOSE DELAYS/DOSE MODIFICATIONS

### 6.1 Infusion-related Reactions including CRS

The predicted mechanism of action of flotetuzumab is the creation of an immunological synapse between the leukemic blast target cell bearing CD123 and immune effectors bearing the T cell specific CD3 complex, leading to T cell activation and killing of the leukemic cell. Activation of T cells is associated with the elaboration of various cytokines. *In vitro* preclinical testing using human PBMCs has suggested that the most vigorous cytokine production is that of IFN- $\gamma$ , but increases in production of TNF- $\alpha$ , IL-2, IL-6, IL-4, and IL-10 were documented. Cytokine production, primarily of IL-6, was also documented in normal cynomolgus monkeys receiving flotetuzumab - a circumstance in which relatively few target cells (mostly CD123-bearing pDCs) were present in the animal's peripheral blood but elimination of those cells was observed. In the cynomolgus monkey, very high doses of flotetuzumab (i.e., 5  $\mu$ g/kg/day) were associated with severe cytokine release of multiple cytokines including IL-6, IFN- $\gamma$ , IL-2, TNF- $\alpha$  and to a lesser extent IL-8 and IL-4, resulting in moribundity or death.

**Infusion-related reactions or Cytokine Release Syndrome (CRS) may occur. Anaphylactic or anaphylactoid-type reactions are possible. Precautions for the management of these reactions should be observed during flotetuzumab administration.**

Infusion-related reactions (including CRS) associated with flotetuzumab administration should be managed according to the standard practice of medicine. General guidelines for the management of such reactions are provided in this section. However, severe reactions may require extraordinary interventions like those that have been required to extinguish the syndrome of cytokine storm or may have anaphylactoid features.

Patients should be monitored closely for the development of IRRs during flotetuzumab infusion; with CRS, ICE and ICANS toxicity assessments recorded in the EMR flowsheets and daily progress notes, as per BMT protocol for patients receiving cellular therapies and cell-engaging therapies. Medications and supportive measures for the treatment of such

reactions should be available for immediate use for an infusion reaction during study drug administration and may include, but are not limited to: subcutaneous (SC) epinephrine (0.3 to 0.5 mL of a 1:1000 solution), antihistamines (e.g., diphenhydramine 25 to 50 mg IV), corticosteroids (e.g., dexamethasone 10 mg IV push or equivalent), IV fluids, vasopressors, oxygen, bronchodilators, and antipyretics. Resuscitation equipment and other supplies for the emergency management of an allergic/toxic reaction must be available. The patient should be treated according to the best available local practices and procedures. All supportive measures consistent with optimal patient care will be provided throughout the study according to institutional standards.

Should symptoms of fever or chills develop it may be difficult or impossible to distinguish among potential causes of the symptoms including underlying leukemia, neutropenic fever, emerging infection, or infusion reaction. Temporarily halting the flotetuzumab infusion to collect cultures, institute antimicrobials, etc., may provide information regarding etiology. If the fever and chills are considered not related (as described in Section 6.3) to the infusion of study drug, the study drug may be reinstated at the same rate of administration after administration of acetaminophen, H2 blockers, and diphenhydramine if not administered previously for premedication. More complex symptom composites may require additional intervention. Please refer to Section 6.3 for management of infusion reactions if the event is considered related to flotetuzumab. If during assessment of IRR/CRS a patient undergoes imaging and/or sample collection, e.g., pleural fluid, intra-articular joint aspiration, or ascitic fluid, a sample may be further evaluated in order to help elucidate etiology.

## **6.2 Premedications and Prophylaxis**

Based on the clinical experience to date, similar findings from other bispecific molecules such as blinatumomab and reported clinical experience with CAR-T therapies, all patients will receive premedication to prevent or mitigate potential infusion-related reactions. Specific pre-treatment regimens are described below (Table 4).

### Prior to the first dose (Week 1):

All patients are to be treated as described in Table 4 below. No steroids should be administered for infusion-related reaction prophylaxis except as indicated below. Patients should receive adequate hydration during study therapy, and the addition of IV fluids to maintain intravascular volume (e.g., 50-100 mL/hr of normal saline) is recommended for at least 48 hours after the start of therapy.

### Prior to Week 2 dosing:

The premedication schedule should be followed as described in Table 4 below. In addition, the same premedications should be considered after consultation with the PI if they are resuming flotetuzumab treatment after a dose interruption lasting > 1 day in Cycle 1.

Steroids should not be administered for infusion-related reaction prophylaxis except as indicated below, but may be used for the treatment of emerging symptoms as clinically appropriate. Tocilizumab (8 mg/kg IV) may be used prophylactically in patients who have had severe IRR or CRS in the first week of dosing upon consultation with the PI. Patients should receive adequate hydration during study therapy, and the addition of IV fluids to

maintain intravascular volume (e.g., 50-100 mL/hr of normal saline) is recommended for at least 48 hours after the start of therapy in Week 2.

Prior to subsequent doses (after Week 2):

The premedication schedule should be followed as described in Table 4 below. Tocilizumab or steroids may be considered after consultation with the PI.

For infusion-related reactions during the course of treatment, supportive care measures should be implemented as outlined in Table 7 below.

IV fluids should be administered for inpatients unless contraindicated and adequate oral hydration should be emphasized for patients treated as outpatients in Cycles 2 and beyond.

Dose interruption:

If dosing is interrupted for > 24 hours during continuous infusion, the premedication schedule should be followed (Table 4).

**Table 4: Premedication Guidelines**

28 day continuous Flotetuzumab infusion schedule				
Medication	Week 1	Week 2	Week 3	Week 4
Acetaminophen (1000mg PO)	Day 1: 30 minutes prior to dosing, then q8 hrs for 48 hours  Day 7 or day of target dose: 30 minutes prior to dose change, then q8 hrs for 48 hours	None	None	None
Diphenhydramine (25-50mg IV or PO) or equivalent	Day 1: 30 minutes prior to dosing, then q8 hrs for 48 hours  Day 7 or day of target dose: 30 minutes prior to dose change, then q8 hrs for 48 hours	None	None	None
Ranitidine (50mg IV) or equivalent	Day 1: 30 minutes prior to dosing, then q8 hrs for 48 hours  Day 7 or day of target dose: 30 minutes prior to dose change, then q8 hrs for 48 hours	None	None	None
Dexamethasone (or equivalent)	Day 1: 10-20mg IV up to 30 minutes before dosing. Then 4mg IV at 12 hours after dosing.  Day 7 or day of target dose: 10mg IV up to 30 minutes prior to dose change, then 4mg 12 hrs later.	None	None	None

28 day continuous Flotetuzumab infusion schedule				
Medication	Week 1	Week 2	Week 3	Week 4
Tocilizumab (8mg/kg IV)	None	After consultation with PI	None	None

### 6.3 Management of Observed Flotetuzumab Infusion Reactions and Infusion-related Adverse Events

The following are treatment guidelines (which may be modified as needed by the responsible Investigator according to the best practices of medicine) for flotetuzumab IRRs including CRS. Early intervention at the first signs of IRR/CRS, including pyrexia, tachycardia, tachypnea and/or hypotension in the absence of alternative etiologies and in consistent temporal relationship to administration of flotetuzumab, should be undertaken.

IRR/CRS is a commonly observed event during treatment with flotetuzumab 89.6% of the 115 patients receiving flotetuzumab monotherapy experiencing at least 1 event of Grade 1-3 IRR/CRS, as of the data cut-off date of 21 April 2020 from the most current MacroGenics IB v9.0. Based on current understanding gained with patients treated with CAR-T cells (which have a T-cell activating mechanism of action in common with flotetuzumab), CRS is likely to be a common toxicity that can be managed through supportive care and anti-cytokine interventions to allow for full activity of T cells during therapy. In the 2019 ASTCT Consensus Guidelines for grading and management of CRS proposed by Lee, et al (18), intensive supportive care and treatment of the underlying cause of the CRS (excessive cytokine production) is recommended before the event must be considered Grade 3 or Grade 4 severity. Adopting this definition of CRS as described in Table 5, and concomitantly modifying the guidelines for management of IRR/CRS (below), will allow for more flexible management of patients who develop CRS and who may nonetheless experience clinical benefit despite the need to manage through mild or moderate infusion reactions while not jeopardizing overall safety.

IRR/CRS will be graded according to the definitions described below in Table 5.

**Table 5: Adapted from the ASTCT CRS Consensus Grading Criteria**

Toxicity Grade	Characteristics
Grade 1	Temperature $\geq 38^{\circ}\text{C}$ , no hypotension or hypoxia.
Grade 2	Temperature $\geq 38^{\circ}\text{C}$ , not requiring vasopressors and/or requiring $\leq 6\text{L}/\text{minute}$ oxygen support.
Grade 3	Temperature $\geq 38^{\circ}\text{C}$ , requiring a vasopressor (with or without vasopressin) and/or requiring $\geq 6\text{L}/\text{minute}$ oxygen support (via high flow nasal cannula, facemask, non-rebreather or Venturi mask).
Grade 4	Temperature $\geq 38^{\circ}\text{C}$ , requiring multiple vasopressors (not including vasopressin) and/or requiring positive pressure ventilation (including CPAP, BiPAP and intubation/mechanical ventilation)

Grade 5	Death
---------	-------

Source: Lee DW, et al. (18)

The above grading scale (Table 5) should be used to grade all infusion reactions in this study, irrespective of the underlying mechanism of the reaction. Certain AEs may occur in temporal proximity to infusion of study drug and therefore, be considered “infusion-related” while not being considered an “infusion reaction;” such events may be graded separately according to CTCAE specific criteria.

IRR/CRS should be managed as described below, when possible. Every attempt should be made to continue the infusion during management of the reaction, however decisions to change or hold the infusion should ultimately be left to the discretion of the treating physician.

**Table 6: Guidelines for Managing Infusion Reactions and Cytokine Release Syndrome\***

Grade/Event	Procedures for Management
Grade 1 Infusion Reactions, including Cytokine Release Syndrome (CRS)	
 
• Slow the infusion rate by 10%-20%;
 
• Monitor the patient for worsening of condition;
 
• Administer IV fluids, diphenhydramine 50 mg IV, acetaminophen 1000 mg PO or ibuprofen 400 mg PO for fever, and oxygen and bronchodilators for mild bronchospasm, as appropriate;
 
• Obtain infectious work-up as clinically indicated (UA, blood cultures, imaging, etc) and consider empiric antibiotics per institutional guidelines
 
• Corticosteroids should not be used for Grade 1 IRR/CRS.
 
• Continue infusion at reduced rate and slowly increase infusion rate to the original rate in 2 steps after stabilization or resolution of symptoms every 4-6 hours, as tolerated. A more gradual increase in the rate of infusion may be undertaken after consultation with the PI.
 

Grade 2 Infusion reactions and infusion-related events	
 
• Slow the infusion rate by 25%-50%;
 
• Administer IV fluids, diphenhydramine 50 mg IV, acetaminophen 1000 mg PO or ibuprofen 400 mg PO for fever, and oxygen and bronchodilators for bronchospasm, as appropriate and if not administered previously;
 
• If not already performed, obtain infectious work-up as clinically indicated (UA, blood cultures, imaging, etc) and consider empiric antibiotics per institutional guidelines
 
• Tocilizumab (8 mg/kg IV) should be used for Grade 2 IRR/CRS that does not resolve with other measures within 2 hours, or that requires the use of supplemental oxygen > 4 L by nasal cannula. Tocilizumab dosing may be repeated in 8 hrs if not improved to Grade 1, with a maximum total of up to 4 doses for each CRS event.
 

Grade/Event	Procedures for Management
	
 
• Corticosteroids may be used for Grade 2 IRR/CRS that does not respond to other measures, including tocilizumab
 
• Continue infusion at reduced rate and slowly increase infusion rate to the original rate gradually by half-rate increments (i.e., if rate is reduced from 5 mL/hr to 2.5 mL/hr increase to ~3.75 mL/hr, then 4.5 mL/hr, then 5 mL/hr) after stabilization or resolution of symptoms every 4-6 hours, as tolerated. A more gradual increase in the rate of infusion may be undertaken after consultation with the PI.
 
• Report as an immediately reportable event (IRE);
 
• Report the event as a serious adverse event (SAE), if appropriate.
 
• Monitor for worsening condition.
 

Grade 3 Infusion Reaction and infusion-related events
	
 
• Stop the infusion,
 
• TO AVOID EXACERBATION OF INFUSION REACTION OR CRS: DO NOT FLUSH THE TUBING – ASPIRATE RESIDUAL DRUG FROM THE PORT LUMEN;
 
• Administer IV fluids, diphenhydramine 50 mg IV, acetaminophen 1000 mg PO or ibuprofen 400 mg PO for fever, and oxygen and bronchodilators for mild bronchospasm, as appropriate.
 
• Provide appropriate circulatory support including vasopressors as medically indicated;
 
• If not already performed, obtain infectious work-up as clinically indicated (UA, blood cultures, imaging, etc) and consider empiric antibiotics per institutional guidelines
 
• Administer tocilizumab if not administered previously. If administered previously, an additional dose may be administered in 8 hours for prolonged or recurrent episodes, with a maximum total of up to 4 doses for each CRS event.
 
• Grade 3 IRR/CRS that is refractory to tocilizumab should be treated with corticosteroids; doses of dexamethasone (or equivalent) of greater than 30 mg may be required.
 
• Resume the infusion at previously tolerated dose once the infusion reaction has resolved or decreased to Grade 1. Increase dose rate to the original rate, per protocol, e.g., 500 ng/kg/day, by increasing the dose in near double increments as tolerated after stabilization or resolution of symptoms every 4-6 hours. A more gradual increase in the rate of infusion may be undertaken after consultation with the PI.
 
• Report the event as a serious adverse event (SAE), if appropriate.
 

Grade/Event	Procedures for Management
	
 
• Discontinue the infusion if not resolved to Grade 1 within 72 hours.
 

Grade 4 Infusion reactions and infusion-related events	
 
• Stop the infusion and disconnect the infusion tubing from the patient;
 
• TO AVOID EXACERBATION OF INFUSION REACTION OR CRS: DO NOT FLUSH THE TUBING – ASPIRATE RESIDUAL DRUG FROM THE PORT LUMEN;
 
• Administer IV fluids, diphenhydramine 50 mg IV, acetaminophen 1000 mg PO or ibuprofen 400 mg PO or paracetamol 1000 mg PO for fever, and oxygen and bronchodilators for mild bronchospasm, as appropriate;
 
• Provide appropriate ventilator and circulatory support as medically indicated;
 
• If not already performed, obtain infectious work-up as clinically indicated (UA, blood cultures, imaging, etc) and consider empiric antibiotics per institutional guidelines
 
• Agents including those listed below have been described in the management of patients with severe complications of cytokine storm and/or severe immune-related adverse events, and may be required:               
 
○ high doses of corticosteroids above dexamethasone 30 mg (or equivalent)
 
○ tocilizumab (anti-IL6 receptor) 8 mg/kg IV, administered every 8 hours as indicated with a maximum total of up to 4 doses for each CRS event
 
 
 
• Notify the PI immediately;
 
• Report the event as an SAE. Patients who have a Grade 4 IRR/CRS should not receive further flotetuzumab.
 

Grade 5 Infusion reactions and infusion-related events	
 
• Notify the PI or designee immediately.
 
• Report the event as an SAE.
 

\* Table provides guidelines but treating physician should follow their discretion to manage and grade CRS/IRR

Other types of adverse reactions may be observed during infusion that are not interpreted as related to cytokine release, but may be related to flotetuzumab. Such reactions should be diagnosed, graded and managed according to best practices.

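### Table 5 places some CRS/infusion reactions in two grades at once, and the Table 6 footnote lets the treating physician grade at discretion although Section 6.3 fixes Table 5 as the scale

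*Combined protocol and SAP*

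**What the plan says.** Section 6.3 names the scale twice. Before Table 5: "IRR/CRS will be graded according to the definitions described below in Table 5". After it: "The above grading scale (Table 5) should be used to grade all infusion reactions in this study". The same section leaves management to clinical judgement: "decisions to change or hold the infusion should ultimately be left to the discretion of the treating physician". The footnote to Table 6 goes further and says the "treating physician should follow their discretion to manage and grade CRS/IRR".

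All grades in Table 5 require a temperature of at least 38°C. The rows that matter here are:

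- **Grade 1:** neither hypotension nor hypoxia.
- **Grade 2:** "not requiring vasopressors and/or requiring" oxygen at 6 L/minute or less. No delivery device is named.
- **Grade 3:** "requiring a vasopressor (with or without vasopressin) and/or requiring" oxygen at 6 L/minute or more, "via high flow nasal cannula, facemask, non-rebreather or Venturi mask".
- **Grade 4:** more than one vasopressor (vasopressin not counted), or positive pressure ventilation.

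Table 6 ties an action to each grade. Grade 1 slows the infusion by 10–20%. Grade 2 slows it by 25–50% and then says: "Continue infusion at reduced rate and slowly increase infusion rate to the original rate gradually by half-rate increments". Grade 3 stops it, with discontinuation if the reaction is not down to Grade 1 in 72 hours. Grade 4 bars any further flotetuzumab.

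CRS grade is a secondary safety endpoint (Section 2.0). It also enters the non-GVHD stopping rule through Section 11.5.1. That rule counts non-hematologic events of Grade 3 or higher, but exempts a Grade 3 infusion reaction that is controlled clinically and is gone within 7 days, leaving no organ damage.

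**The concern.** A grading scale should put each reaction in one grade, and the person recording the grade should not be free to depart from the scale. Section 6.3 misses on both counts.

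First, two pairs of rows in Table 5 overlap: Grades 2 and 3 at a single oxygen flow, and Grades 1 and 2 because the Grade 2 wording does not ask for hypotension. Second, the footnote extends discretion from management to grading, against the two statements in the body of Section 6.3.

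The grade determines a reported secondary endpoint, the recommended infusion action, whether a reaction counts toward the stopping rule, and whether Table 6 bars further drug. The study is open-label, single-arm and single-center, so there is no comparator arm graded in the same way to absorb inconsistent grading.

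**Working it through.** No sample-size or power figure is involved. The check compares the rows and then counts what a changed grade does.

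**1. Overlap between Grades 2 and 3.** A flow of 6 L/minute or less and a flow of 6 L/minute or more share one value: exactly 6. Two passages narrow this. The Grade 3 flow limit is tied to named devices, and the ordinary low-flow cannula is not among them. The Grade 2 row of Table 6 treats a need for more than 4 L by nasal cannula as still Grade 2. So 6 L/minute by ordinary cannula reads as Grade 2. What remains is a listed device, such as a facemask, at exactly 6 L/minute. It meets the Grade 3 row, and also the Grade 2 row, which names no device.

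**2. Overlap between Grades 1 and 2.** Take a patient with fever only, normal blood pressure and no oxygen. The Grade 1 row fits. The first limb of the Grade 2 row asks only that vasopressors are not needed, and that is true too. Because the limbs are joined by and/or, meeting one is enough.

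**3. Grades 3 and 4.** Table 5 has no overlap here: one vasopressor against several, or oxygen by mask or high-flow cannula against positive pressure ventilation. Only the footnote leaves this line open.

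**4. Effect on the stopping-rule count (Section 11.5.1).** Take a reaction at least possibly attributable to treatment, in a patient with no other counted toxicity:

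| Recorded grade | Exemption conditions met | Conditions not met |
|---|---|---|
| 1 or 2 | 0 | 0 |
| 3 | 0 | 1 |
| 4 | 1 | 1 |

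- Grade 1 versus 2: no change in the count.
- Grade 2 versus 3: a change of 0 if the conditions are met, 1 if not.
- Grade 3 versus 4: a change of 1 if the conditions are met, 0 if not.

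The first boundary is 2 events in 5 patients (Section 11.6). Crossing a boundary pauses enrollment for QASMC review; it does not end the trial automatically.

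**5. Effect on a reported CRS grade rate.** One re-graded patient moves the rate by 1/n, where n is the number treated. At n = 25, 1/25 = 4.0 percentage points. At n = 15, the end of stage 1, 1/15 = 6.7 points. The 25 is the evaluable target for efficacy. Safety covers everyone who receives any drug (Sections 5.5 and 11.8) and non-evaluable patients are replaced, so n can exceed 25 and the shift would then be below 4 points.

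**6. How often.** The documents do not say how often oxygen would be given at exactly 6 L/minute by a listed device, or how often discretion would change a grade. For context, Section 1.2.1 reports 9 of 81 patients (9/81 = 11.1%) with a Grade 3 reaction and none that was life-threatening or fatal. Section 1.1.7 gives Grade 3 CRS as 16% in relapsed and 3% in primary refractory patients.

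**The case against.** The strongest reply is that little turns on this. The oxygen overlap is one flow value on a listed device. Section 6.3 calls its treatment guidance modifiable and leaves infusion decisions to the physician, so slowing and stopping are starting recommendations, not binding orders. The footnote names no rival scale and sits under a management table with no grading criteria, so it could mean ordinary judgement in applying Table 5. Section 6.1 accepts that fever and chills can be hard to separate from infection or leukemia. The line between Grades 3 and 4 is observable, and nothing suggests physicians would ignore it.

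Most of this stands as a limit on size. Discretion over management is a stated design choice and is not in dispute. It does not remove the defect: a physician can depart from the recommended action and still record the grade by Table 5. Judging whether a fever is an infusion reaction differs from choosing its grade. As worded, the footnote gives discretion over the grade itself, which the body of Section 6.3 does not.

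A reader might infer that every patient at 6 L/minute is ungradable. The device list and the cannula wording in Table 6 do not support that. A reader might also infer that Appendix C, which names CTCAE v5.0 for all toxicity reporting, creates a competing scale for CRS. Sections 2.0 and 6.3 assign CRS to the ASTCT criteria and Table 5, and that specific text governs.

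**Conclusion.** The concern holds: the grading text is wrong as written. Table 5 has two overlaps, and the footnote contradicts the section it belongs to.

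The size is small. Each re-graded patient shifts a reported CRS grade rate by one over the number treated. The stopping-rule count changes only in the cells shown in the table, which will be rare. The CR/CRi primary endpoint and the sample size are untouched. A reader might infer that the safety monitoring is unreliable or that grades will be steered. The documents give no basis for either: Grades 3 and 4 are cleanly separated in Table 5, no life-threatening reaction was reported among the 81 patients, and a crossed boundary leads to committee review.

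The conclusion assumes that the inequality signs in Table 5 are as they read in the document and that the footnote means what it says about grading. Frequency cannot be estimated from the documents.

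**What to change.** 1. **Table 6 footnote:** delete *and grade*. Keep the discretion over management.
2. **Table 5, oxygen limits:** make them exclusive, with Grade 2 at 6 L/minute or less and Grade 3 above 6 L/minute. Alternatively, state that any of the listed devices means Grade 3.
3. **Table 5, Grade 2:** require the sign itself, for example *hypotension managed without vasopressors, and/or hypoxia needing no more than 6 L/minute of oxygen*. This removes the overlap with Grade 1.

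Two clerical items can go in at the same time. Section 11.5.1 could say that infusion reactions and CRS are graded by Table 5. Section 6.2 points to Table 7 (acute GVHD) for managing infusion reactions where Table 6 is meant.

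The cost is two words in a footnote and two table rows in the next amendment, plus one sentence and one table number if the clerical items are taken. No patients, visits or data are added.
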